## 6.6 RSV SURVEILLANCE: FIRST SEASON

### 6.6.1 Pre-RSV Season Surveillance Study Visit

The Pre-RSV Season Study Visit is not required if the Day 56 Visit is conducted on or after October 1; the samples collected at the Day 56 Visit are sufficient for the Pre-RSV Season Study Visit. Otherwise, an in-person visit is expected of participants during the Pre-RSV Season for collection of a blood sample, nasal wash sample and/or nasosorption strip for RSV antibody assays.

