### *Infectivity*

1. To determine the peak titer of vaccine virus shed and duration of virus shedding by each participant
2. To assess the proportion of vaccinated participants infected with study vaccine (If < 70% of RSV-seronegative vaccinees are infected with vaccine virus, the study product will be considered over-attenuated.)

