## **3 STUDY DESIGN**

The study will be double-blind, randomized, and placebo-controlled. Participants in groups 1 and 2 will be block-randomized in groups of 3 at a ratio of 2:1 to receive vaccine or placebo, respectively. The vaccine will be evaluated in a stepwise fashion beginning with RSV-seropositive children (Group 1) and proceeding sequentially in RSV-seronegative children (Group 2). For the purpose of this study, RSV-seropositive is defined as having a serum neutralizing antibody titer of  $\geq 1:40$ , and RSV-seronegative is defined as having a serum neutralizing antibody titer of  $< 1:40$ . This definition has been used in previous evaluations of live-attenuated RSV vaccines (11, 24, 35). In these previous studies, live-attenuated RSV vaccines were highly restricted in replication and poorly immunogenic in children with titers  $\geq 1:40$  but were far less restricted in replication and highly immunogenic in children with titers  $< 1:40$ . These data suggest that this neutralizing antibody cutoff can distinguish effectively between RSV-experienced and RSV-naïve children.

The study will proceed to group 2 if there are not more than 2 vaccine-associated solicited AEs and no vaccine-associated LRIs in RSV-seropositive children. If 3 or more RSV-seropositive children have respiratory or febrile illness that coincides with shedding of  $> 10^{2.5}$  PFU of vaccine virus as detected by culture, then we will enroll an additional 15 RSV-seropositive children to continue evaluating the safety, infectivity, and immunogenicity of the vaccine virus.

Enrollment occurs at the time of inoculation with study product, Day 0, and will occur between April 1 and October 31 to avoid the time during which wt RSV typically circulates in the community ([Appendix V](#), Figure 6). Accrual will stop prior to November 1.

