#### **4.3 INCLUSION CRITERIA FOR RSV-SERONEGATIVE INFANTS & CHILDREN**

Potential RSV-seronegative participants must meet all of the following inclusion criteria to be enrolled in this study:

- 4.3.1.  $\geq$  6 months of age and  $<$  25 months of age at the time of inoculation
- 4.3.2. Screening and pre-inoculation serum specimens for RSV-neutralizing antibody are obtained no more than 42 days prior to inoculation
- 4.3.3. Seronegative for RSV antibody, defined as serum RSV-neutralizing antibody titer  $<$  1:40
- 4.3.4. In good health based on review of the medical record, history, and physical examination at the time of inoculation
- 4.3.5. Received routine immunizations appropriate for age based on the ACIP Recommended Immunization Schedule for Children and Adolescents Aged 18 Years or Younger
- 4.3.6. Growing normally for age as demonstrated on a standard growth chart, AND
  - If  $<$  1 year of age: has a current height and weight above the 5th percentile for age
  - If  $\geq$  1 year of age: has a current height and weight above the 3rd percentile for age
- 4.3.7. Expected to be available for the duration of the study
- 4.3.8. Parent/guardian is willing and able to provide written informed consent

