## 6.4 ENROLLMENT

### 6.4.1 Enrollment - Inoculation (Day 0)

Enrollment will occur between April 1 and October 31 to avoid the RSV season. For the purpose of this protocol, enrollment will correspond to inoculation with investigational product, which occurs on study day 0, and must be completed at a CIR office site or pediatric practice where emergency supplies are available. Prior to inoculation, an authorized prescriber will provide a request for study product to the unblinded dispenser. The request must include the information outlined in the MOP.

The ICD will be obtained from the parent/guardian of each child who participates in this study prior to the performance of any study procedures or inoculation. If not previously obtained, then the ICD will be completed on the day of enrollment. The child's parent/guardian will be encouraged to ask questions and complete a comprehension assessment to evaluate understanding of the study. Study staff will use incorrect answers from the comprehension assessment to identify those areas of the ICD that need further review with the parent/guardian. This will help ensure that the parent/guardian has sufficient understanding of the study process before the ICD is signed.

If the participant is noted to have any of the following on enrollment day, inoculation must be deferred:

- fever (temporal or rectal temperature of  $\geq 100.4^{\circ}\text{F}$ ), or
- URI or LRI symptoms or signs (including but not limited to rhinorrhea, cough, or pharyngitis), or
- nasal congestion significant enough to interfere with successful inoculation, or
- otitis media.

If the inoculation for an RSV-seropositive participant has to be deferred to the following calendar year, or if the 42-day window from screening to inoculation is exceeded for an RSV-seronegative participant, then the infant or child must be rescreened.

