**Table 12: Day 56 Visit Procedures – RSV-Seronegative Children**

Day 56 Visit (+7 Days)	
Administrative Tasks	
 
• Provide first study compensation payment
 

Clinical Tasks	
 
• Obtain and document from parent/guardian the participant's interim history from midnight of the 28th day through the 56th day following inoculation, including: 
 
▪ visits to medical provider/hospitalizations
 
▪ medications and/or immunizations
 
▪ signs and symptoms of illness meeting SAE criteria
 
 
 
• Address any concerns
 
• Review safety data
 
• Document findings
 

Laboratory Tasks	Blood Collect blood for: 
 
• Serum antibodies to RSV
 

	Nasosorption SAM Strip and/or Nasal Wash Collect nasosorption strip for: 
 
• RSV antibody assays
 
 
Note: The nasosorption must be performed prior to the nasal wash.
 
Collect nasal wash for:
 
• RSV antibody assays
 

Follow-up Preparation	
Follow-up depends on when, during the calendar year, the Day 56 Visit is conducted. If Day 56 Visit is conducted:
 
 
• Prior to October 1 
 
▪ schedule Pre-RSV Season Visit (Section 6.6.1)
 
 
 
• On or after October 1 
 
▪ Day 56 Visit will also be the Pre-RSV Season Visit
 
▪ Review plans for weekly contact during the RSV Season Surveillance Period (Section 6.6.2)
 
 
 

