### 6.8 ILLNESS VISIT

The timeframe after staff notification in which the Illness Visit must occur depends on the study phase and the grading of the fever and respiratory symptoms per Section 8.2 and If the Illness Visit occurs on a day concurrent with an in-person study visit, a single nasal wash collection is required and adventitious agent testing will be requested. All symptoms will be followed until resolution or deemed stable or chronic by appropriate medical personnel (e.g., medical doctor or nurse practitioner). Illness Visits may occur during any of the study phases.

If the acute or post-acute phases overlap the surveillance period (between November 1 and March 31), then the timelines for the acute and post-acute phases will be used.

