## **9.2 OUTCOME MEASURES**

### **9.2.1 Primary Outcome Measures**

*Safety: Types and grades of study product-related:*

- Solicited AEs as defined in Appendix IV from Study Days 0-10 for RSV-seropositive and Study Days 0-28 for RSV-seronegative participants
- Unsolicited AEs from Study Days 0-10 for RSV-seropositive and Study Days 0-28 for RSV-seronegative participants
- SAE (Section 8.1.2) from Study Days 0-28 for RSV-seropositive and Study Days 0-56 for RSV-seronegative participants

*Infectivity:*

- Infection with RSV as defined as
  - 1) vaccine virus identified in a nasal wash from Study Days 0-10 for RSV-seropositive and Study Days 0-28 for RSV-seronegative (a binary outcome based on nasal washes done throughout the study period; Day 0 nasal wash will be counted as baseline); or
  - 2)  $\geq 4$ -fold rise in RSV neutralizing antibody titer from Study Days 0-28 for RSV-seropositive and Study Days 0-56 for RSV-seronegative subjects
- Peak titer of vaccine virus shed from Study Days 0-10 for RSV-seropositive and Study Days 0-28 for RSV-seronegative subjects
- Duration of virus shedding in nasal washes as determined by a) culture and b) RT-PCR from Study Days 0-10 for RSV-seropositive and Study Days 0-28 for RSV-seronegative subjects

*Immunogenicity:*

- $\geq 4$ -fold rise in RSV-neutralizing antibody titer from study entry to Study Day 28 for RSV-seropositive and from study entry to Study Day 56 for RSV-seronegative subjects
- $\geq 4$ -fold rise in IgG antibody responses to RSV F glycoprotein (ELISA) from study entry to Study Day 28 for RSV-seropositive and from study entry and Study Day 56 for RSV-seronegative subjects

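### Group 2 Day 56 sera can be drawn in the RSV season: a wild-type rise can then count as vaccine infection, and the same serum can serve as the pre-season baseline

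*Combined protocol and SAP*

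**What the plan says.** **Dates.** Section 6.4.1: "Enrollment will occur between April 1 and October 31 to avoid the RSV season". Section 3: "Accrual will stop prior to November 1". Section 6.5.2.5 places the Group 2 Day 56 visit between Day 56 and Day 63. Section 6.6.2 runs surveillance from November 1 to March 31.

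**Infection endpoint.** Section 9.2.1 defines infection as vaccine virus in a nasal wash or a fourfold or greater "rise in RSV neutralizing antibody titer from Study Days 0-28 for RSV-seropositive and Study Days 0-56 for RSV-seronegative subjects". The second limb does not mention wild-type RSV. Under the Infectivity objectives in Section 2.1, if fewer than 70% "of RSV-seronegative vaccinees are infected with vaccine virus, the study product will be considered over-attenuated".

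**Pre-season serum.** Section 6.6.1: "The Pre-RSV Season Study Visit is not required if the Day 56 Visit is conducted on or after October 1". Table 12 agrees for any such visit: "Day 56 Visit will also be the Pre-RSV Season Visit". Neither gives an end date. Table 13 places the pre-season visit in October 1 to 31.

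**Seasonal criterion.** Section 6.10.3 treats a fourfold rise between the pre- and post-season sera as the sign of wild-type infection.

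**Overlap of phases.** Section 6.6.2 accepts that surveillance may overlap the Acute and Post-Acute Phases and requires the evaluations of every relevant phase. Section 6.8 says that on overlap "then the timelines for the acute and post-acute phases will be used".

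**The concern.** The calendar keeps inoculation out of the season but not the serum that defines the endpoint. For a child inoculated in late September or October, a November or December rise meets two descriptions: vaccine infection under 9.2.1 and wild-type infection under 6.10.3. Nothing decides between them. The protocol draws this distinction elsewhere: one stopping criterion in Section 8.3 makes an exception for RSV confirmed as wild type. Section 9.5.1 allows exclusion from the immunogenicity analysis for disallowed treatments but does not mention wild-type infection.

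Three results are at stake:

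- The 70% rule uses vaccinees only, so placebo seroconversions do not correct it.
- The one-sided Fisher test of fourfold responses loses contrast when placebo recipients seroconvert to wild-type virus.
- A wild-type infection before a reused Day 56 serum raises the baseline, so the pre/post-season criterion can miss it.

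Serology may carry much of the infection endpoint. Section 1.2.1.1 reports that the closest predecessor, at 10^5 PFU in 15 seronegative vaccinees, had 7% shedding by culture and 53% with a neutralizing response.

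**Working it through.** **1. Dates**

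| Quantity | Arithmetic | Result |
|---|---|---|
| Latest nominal Day 56 | October 31 + 56 days | December 26 |
| Latest draw in window | October 31 + 63 days | January 2, 62 days after November 1 |
| Last inoculation with nominal Day 56 by October 31 | October 31 − 56 days | September 5 |
| Same, if the full +7 window is used | October 31 − 63 days | August 29 |
| Enrolment dates, April 1 to October 31 | count | 214 |
| Dates with nominal Day 56 on or after November 1 | September 6 to October 31 | 56 (26%) |
| Same, with the +7 window | August 30 to October 31 | 63 (29%) |

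**2. Part of the season without scheduled virus-detection washes**

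Section 6.5.2.1 schedules virus-detection washes to Day 28, with daily contact over the same period. An October 31 inoculation reaches Day 28 on November 28. From there to the draw is 28 days (Day 56) or 35 days (Day 63). That is the longest in-season stretch without a scheduled wash.

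**3. The plan's own figures**

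Full enumeration of the one-sided Fisher exact test (20 versus 10, alpha 0.05) at the five rows of Table 26 gives power 0.806, 0.797, 0.795, 0.801 and 0.797. The stated 80% is reproduced.

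**4. Effect on the 70% rule**

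Let p be the true vaccine take and c the probability of a wild-type rise by the Day 56 draw, averaged over all Group 2 children. Then

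apparent take = p + (1 − p) × c, with c = (share enrolled late) × (share of late children with a wild-type rise).

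With 20 vaccinees, 14 is exactly 70%, so the rule is cleared at 14 or more. Neither factor of c is in the documents; all values below are assumptions. As a rough guide to the second factor, nominal Day 56 for inoculations from September 6 to October 31 averages 27.5 days into the 151-day season (18%). If 50 to 70% of children were infected per season at a uniform rate, 9 to 13% would be infected by then.

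| Late share | Wild-type rise in late children | c | Apparent take at p = 0.60 | P(at least 14 of 20) |
|---|---|---|---|---|
| none | none | 0 | 0.60 | 0.25 |
| 0.26 | 0.10 | 0.026 | 0.61 | 0.28 |
| 0.50 | 0.10 | 0.05 | 0.62 | 0.31 |
| 0.50 | 0.20 | 0.10 | 0.64 | 0.38 |
| 0.50 | 0.30 | 0.15 | 0.66 | 0.45 |

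With 14 vaccinees, the lower end of the range in Table 1, the rule is cleared at 10 or more. At p = 0.60 the chance is 0.28 at c = 0, 0.33 at c = 0.05 and 0.39 at c = 0.10.

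**5. Effect on the vaccine-placebo test**

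Apply the same c to both arms in the first row of Table 26 (0.05 versus 0.52). At c = 0.05 the proportions become 0.05 + 0.95 × 0.05 = 0.098 and 0.52 + 0.48 × 0.05 = 0.544. Power falls from 0.81 to 0.71. At c = 0.10 it is 0.64.

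**The case against.** **Surveillance continues during overlap.** A reader might infer from 6.8 and Table 16 that Post-Acute illness visits are limited to SAEs, leaving mild wild-type infection unsampled. The documents do not support that. Section 6.6.2 keeps every phase's evaluations running, 6.8 gives precedence only to timelines, and the Post-Acute and surveillance timelines in Table 16 are both 3 days. Section 6.10.2 also provides culture and rRT-PCR on illness washes through Day 56. This stands: the undetected exposure is mainly infection that is not medically attended between Day 28 and the draw, not 62 days without sampling. It does not cure the endpoint, because no text says that a detected wild-type infection removes a child from the serological count.

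**The size is assumed.** This also stands. Section 1.1.1 places epidemics in late winter and early spring, and the upper rows of the table in step 4 need both assumptions to be unfavourable.

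**Placebo recipients reveal exposure.** Blocks of three give calendar-matched controls, and the study calls itself exploratory. That makes contamination visible but does not adjust the single-arm 70% rule.

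**A virus-only definition would err the other way.** In the predecessor at 10^5 PFU, 7% of 15 is 1 child and 53% is 8, so at least 7 of 15 responded without shedding by culture. Suppose true take is 80%, half of children are late and 25 to 50% of takes are serology-only (all assumed). Requiring virus recovery in late children lowers apparent take to 0.80 × (1 − 0.5 × 0.25) = 0.70, or 0.80 × (1 − 0.5 × 0.50) = 0.60. P(at least 14 of 20) then falls from 0.91 to 0.61 or 0.25. Virus recovery therefore belongs in a sensitivity analysis, not in the primary definition.

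**Details are left to an analysis plan.** Section 9.5.1 says so, but the text available contains no attribution rule.

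**Conclusion.** The point holds for Group 2 children inoculated after September 5 (after August 29 if the full window is used). Their Day 56 serum can be drawn in the protocol's own RSV season, a rise by then counts as infection whatever its cause, and the same serum may serve as the pre-season baseline in conflict with Table 13. The direction is clear: apparent take goes up, the vaccine-placebo contrast goes down, and early wild-type infections can drop out of the seasonal serological criterion.

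The size is open. At a true take of 60%, the chance of clearing the 70% rule moves from 0.25 to 0.28–0.31 under milder assumptions and to 0.38–0.45 under unfavourable ones. Accrual timing and wild-type incidence decide which applies, and the documents give neither.

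Three stronger readings do not follow:

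- *The 70% rule is the trial's only numeric rule.* It is not: Section 3 sets counts for moving to Group 2, and Section 8.3 sets stopping counts.
- *Natural infection is lost altogether from the season-1 comparison.* Medically attended illness is still sampled virologically, so the loss is confined to the serological criterion.
- *Baseline sera need a matching restriction in spring.* Section 4.3 says "Screening and pre-inoculation serum specimens for RSV-neutralizing antibody are obtained no more than 42 days prior to inoculation", which would allow a February 18 serum for an April 1 inoculation. But Group 2 follows Group 1, whose criteria for proceeding in the Protocol Summary include LRIs through Day 28. In one accrual year Group 2 cannot start before April 29 (April 1 + 28 days), and 42 days earlier is March 18. This does not justify a separate requirement.

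**What to change.** 1. **Sections 9.2.1 and 9.5.1.** State that a child with wild-type RSV identified before the Day 56 draw is not counted as vaccine-infected on serology alone, nor as a vaccine responder. Otherwise keep the primary definition. Prespecify that the infection proportion, its comparison with 70% and the fourfold response are repeated (a) in children whose Day 56 serum was drawn by October 31, and (b) with infection based on vaccine virus recovery only for later draws. Show both beside the placebo fourfold rate for the same calendar period.
2. **Section 6.6.1 and Table 12.** Treat the Day 56 serum as the pre-season baseline only if drawn October 1 to 31, in line with Table 13. For later draws, identify wild-type infection between November 1 and Day 56 by culture or rRT-PCR, and flag these children in the season-1 serological analysis.
3. **Section 6.8 and Table 16.** Reconcile with 6.6.2, so that it is clear that the medically attended surveillance triggers apply from November 1 while phases overlap.

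Settle this before Group 2 results are seen. Section 6.3 allows the code to reach clinical staff once a block completes its Acute Phase, so later reclassification could be made with treatment known.

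The cost is protocol and analysis-plan wording, a little more analysis, and the loss of serological season-1 classification for a few late-enrolled children.

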**Table 13: Pre-RSV Season Surveillance Study Visit Procedures**

Pre-RSV Season Study Visit (October 1 through October 31 of enrollment year)	
Clinical Tasks	
 
• Document findings related to study procedure
 

Laboratory Tasks	
Collect blood for:
 
 
• Serum antibodies to RSV
 

Nasosorption SAM Strip and/or Nasal Wash	
Collect nasosorption strip for:
 
 
• RSV antibody assays
 
• Note: The nasosorption must be performed prior to the nasal wash.
 
 
The nasal wash must be obtained prior to administering the study product.
 
Collect nasal wash for:
 
 
• RSV antibody assays
 

Follow-up Preparation	
 
• Review plans for weekly contact during the RSV Season Surveillance Period (see Section 6.6.2)
 

## 6.6.2 Weekly Contact for Surveillance during the RSV Season

Based on previous data regarding the seasonality of RSV in the Baltimore, MD, area ([Appendix IV](#), Figure 6), surveillance for RSV-associated disease will be conducted between November 1 and March 31 during the first RSV season following receipt of study product. For some RSV-seronegative participants, surveillance during the first RSV season may overlap with the Acute and/or Post-Acute study phases. In this case, all evaluations required for each of the relevant phases of the study will be conducted.

During the first RSV season following receipt of study product, participants enrolled in this study will be monitored for symptomatic, medically attended, RSV-like illnesses listed below via weekly telephone or email communication or an in-person visit. (Rhinorrhea and cough need not meet the [Appendix IV](#) criteria if they are documented by the health care provider):

- Medically attended fever
- Medically attended URI
- Medically attended otitis media
- Medically attended LRI

An Illness Visit will be scheduled within 3 days of study staff notification of any of these events (Section [6.8](#)).

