For group 1, RSV-seropositive participants, the duration of participation in the initial phase of the study is 28 days. The initial phase consists of an Acute Phase from inoculation through the 10th day after inoculation, and a Post-Acute Phase from the 11th day through the 28th day after inoculation. For group 2, RSV-seronegative participants, the duration of participation in the initial phase of the study is 56 days. The initial phase consists of an Acute Phase from inoculation through the 28th day after inoculation, and a Post-Acute Phase from the 29th day through the 56th day after inoculation.

During the Acute Phase, the participants' parents/guardians will be contacted daily. These contacts will consist either of an in-person evaluation of interim medical history, clinical assessment, and nasal rinse, or an interim medical history conducted by a mutually agreed upon communication method. During the Acute Phase, the participants will be evaluated for AEs or SAEs. Participants who have a febrile or respiratory illness or otitis media will have a study visit to perform a nasal rinse. The nasal rinse will be tested for RSV and for other respiratory pathogens that are considered adventitious agents. During the Post-Acute Phase, study participants' parents/guardians will be instructed to contact the study staff if any SAEs occur. The RSV-seropositive participants will have a scheduled follow-up visit on the 28th day after inoculation, and the RSV-seronegative participants will have a scheduled follow-up visit on the 56th day after inoculation. The schedules of evaluations during the Acute Phase and Post-Acute Phase are shown in Appendix II, [Table 30](#).

For the RSV-seronegative participants (group 2), the study has a third phase that assesses the incidence and severity of illness suggestive of RSV occurring during the RSV season following inoculation. During the RSV Season Surveillance Period, encompassing November 1 to March 31, study staff will make weekly contact with the participants' parents/guardians to identify medically attended episodes of fever, URI, LRI, or otitis media. Participants who have such an episode will have an in-person evaluation of interim medical history, clinical assessment, and nasal rinse to evaluate for RSV and other respiratory pathogens that are considered adventitious agents (Appendix III).

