**Table 16: Illness Visit Timeframe**

Illness Visit Timeframe			
Phase	Symptoms	Grade	Visit Timeframe
Acute	Fever, otitis media or URI	1	Within 3 days
Acute	Fever, otitis media or URI	$\geq 2$	Within 2 days
Acute	LRI	Any	Within 1 day
Post-Acute	SAE that meets study pause or stop criteria (Section 8.3)	$\geq 2$	Within 3 days
RSV Season Surveillance	Medically attended fever, otitis media, URI or LRI	$\geq 2$	Within 3 days

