### 8.2.1 AE Grading

**Table 21: Grading for Adverse Events**

Severity	Defined
Grade 1 Mild	No medical intervention required; may include over-the-counter medications managed by the participant or caregiver for treatment of symptoms
Grade 2 Moderate	Outpatient medical intervention by a health care provider required; may include use of over-the-counter and/or prescription medications
Grade 3 Severe	Prolonged medical intervention and/or hospitalization required
Grade 4 Life threatening	Illness requiring hospitalization with intensive care
Grade 5 Death	Event resulting in fatal outcome to the participant

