## 9.2.2 Secondary Outcome Measures

- The frequency and severity of symptomatic, medically attended respiratory and febrile illness in the RSV-seronegative (group 2) vaccine and placebo recipients who experience natural infection with wt RSV during the first RSV season and through the second RSV season for group 2 subjects who participate in a second RSV season surveillance.
- The antibody responses in the RSV-seronegative vaccine and placebo recipients who experience natural infection with wt RSV during the first RSV season and during a second RSV season for those who choose to participate.
- The quality and epitope specificity of RSF F-specific antibody

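### Table 16 lists the surveillance Illness Visit only for Grade 2 or higher events, while Sections 3 and 6.6.2 require it for any medically attended event, so some mild episodes may have no RSV test

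*Combined protocol and SAP*

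**What the plan says.** Three places govern the Illness Visit during RSV season surveillance in group 2.

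- **Section 6.6.2** lists four medically attended events (fever, URI, otitis media, LRI) and continues: "An Illness Visit will be scheduled within 3 days of study staff notification of any of these events". It states no grade and refers the reader to Section 6.8.
- **Section 3** describes the same surveillance: "Participants who have such an episode will have an in-person evaluation of interim medical history, clinical assessment, and nasal rinse to evaluate for RSV". Again there is no grade.
- **Section 6.8, Table 16** has one surveillance row, "Medically attended fever, otitis media, URI or LRI", with a grade entry of ≥ 2 and a limit of 3 days. The Acute phase has a Grade 1 row for fever, otitis media or URI and a row for LRI of any grade. Surveillance has neither.

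Section 6.8 introduces the role of grade as follows: "The timeframe after staff notification in which the Illness Visit must occur depends on the study phase and the grading of the fever".

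The visit supplies virology for the first secondary outcome in Section 9.2.2, "The frequency and severity of symptomatic, medically attended respiratory and febrile illness in the RSV-seronegative (group 2) vaccine and placebo recipients", restricted to those with natural wild-type RSV infection in the first season and, for those who continue, the second.

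**The concern.** The trigger for the nasal wash depends on which section staff apply. Table 14 tells them to schedule an Illness Visit where one is warranted. Someone who checks Table 16 for a Grade 1 event in the surveillance phase finds no entry.

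The secondary outcome concerns both how often attended RSV illness occurs and how severe it is. If the virological test is itself triggered by severity, the mild end of the distribution is lost from the confirmed episodes in both arms. If the share of Grade 1 illness also differs between arms, as it might if vaccination makes RSV illness milder, the loss is unequal. Part of a difference in severity would then appear as a difference in the frequency of confirmed illness.

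**Working it through.** The plan gives no figure on this point to reproduce. The check is a comparison of text followed by an illustration with assumed inputs.

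**Step 1: can a medically attended event be Grade 1?**

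- *Fever.* Table 22 grades by temperature, whatever care was sought. An attended fever of 100.4 to 101.4°F is Grade 1.
- *URI, otitis media, LRI.* Table 21 defines Grade 1 as "No medical intervention required; may include over-the-counter medications managed by the participant or caregiver for treatment of symptoms" and Grade 2 as "Outpatient medical intervention by a health care provider required; may include use of over-the-counter and/or prescription medications". A child seen by a provider who needed no intervention fits Grade 1. A child who was treated fits Grade 2.
- Table 20 refers to LRIs of every grade in surveillance when it sets medication recording, so low-grade events are foreseen. Section 6.6.2 and Table 20 also relax the Appendix IV criteria in this phase, which widens capture towards milder illness.

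Attended Grade 1 events are therefore possible. They are mainly low fevers and visits without intervention. A low fever accompanied by a Grade 2 URI, otitis media or LRI would be washed under either rule.

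**Step 2: what does a Grade ≥ 2 trigger do to the counts?**

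Inputs from the plan: 20 vaccinees and 10 placebo recipients (Section 9.3.1, upper end of enrolment). Assumed inputs, because the documents give neither: *r*, the true rate of attended wild-type RSV illness, equal in both arms; and *g*, the share of those illnesses that is Grade 1.

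- Tested illnesses in an arm = n × r × (1 − g)
- Ratio of tested rates, vaccine to placebo = (1 − g_V) / (1 − g_P)

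With r = 0.30, testing every attended event gives 20 × 0.30 = 6.0 and 10 × 0.30 = 3.0 expected illnesses, a rate ratio of 1.00. With only Grade ≥ 2 tested:

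| Grade 1 share, vaccine / placebo | Tested, vaccine | Tested, placebo | Ratio of rates |
|---|---|---|---|
| 0% / 0% | 6.0 | 3.0 | 1.00 |
| 10% / 10% | 6.0 × 0.90 = 5.4 | 3.0 × 0.90 = 2.7 | 1.00 |
| 30% / 30% | 6.0 × 0.70 = 4.2 | 3.0 × 0.70 = 2.1 | 1.00 |
| 30% / 10% | 6.0 × 0.70 = 4.2 | 3.0 × 0.90 = 2.7 | 0.70/0.90 = 0.78 |
| 50% / 20% | 6.0 × 0.50 = 3.0 | 3.0 × 0.80 = 2.4 | 0.50/0.80 = 0.62 |

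The ratio does not depend on r; values of 0.20 and 0.50 give the same column. If the larger Grade 1 share were in placebo, the ratio would move the other way: 10% versus 30% gives 0.90/0.70 = 1.29.

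Because allocation is 2:1, the comparison has to be made on rates. Equal counts would not mean equal frequency: 5 of 20 is 25%, and 5 of 10 is 50%.

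**Step 3: severity.** Under a Grade ≥ 2 trigger the Grade 1 share among wash-confirmed surveillance episodes is zero in each arm, whatever the true share. This happens even when the ratio of rates is undistorted.

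**Step 4: does serology replace the wash?** Section 6.10.3 infers wild-type infection from a ≥ 4-fold rise between the pre- and post-season samples. That identifies an infected child, not which of several attended episodes was RSV. Section 6.6.1 also lets a Day 56 sample serve as the pre-season sample. For a child inoculated on October 31, Day 56 is December 26, almost two months into surveillance.

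**The case against.** The strongest reply is that Table 16 sets timing and not entitlement. Its title and the sentence in Section 6.8 tie grade to the visit timeframe. The obligation itself, in Sections 3 and 6.6.2, has no grade limit, and Section 6.6.2 carries its own 3-day limit. Section 6.10.2 and Table 32 add no grade limit. The Post-Acute row also shows ≥ 2, beside an SAE meeting pause or stop criteria, where a grade floor does little work, so the entry may not be deliberate. This stands in part. A reader might infer that Grade 1 children are denied a wash; the documents do not say so. The table is silent where the Acute rows are explicit, and that leaves staff with two defensible readings.

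The second reply is that the gap is narrow. Table 21 puts provider intervention at Grade 2, even when it uses only over-the-counter medication, so many attended non-fever illnesses would be washed anyway. This stands and limits the size.

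The third reply is that the illnesses are not lost. Table 20 records every medically attended fever, URI, otitis media and LRI on the CRF without a grade threshold, and serology can show the infection. Section 6.10.3 says the serological result will permit comparison of the rate and severity of RSV illness. This also stands: a reader might infer that vaccine-arm illness would drop out of the outcome, and the documents do not support that. What is missing is the link between a recorded episode and RSV. Without it, a summary would either count all attended illness in seroconverters, including illness from other viruses, or count only wash-confirmed episodes, which the trigger has selected by severity.

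**Conclusion.** The contradiction is real. Sections 3 and 6.6.2 require a visit for any attended event; the surveillance row of Table 16 lists only Grade ≥ 2. If staff follow the table, some attended Grade 1 episodes have no virological result, and wash-confirmed illness is truncated at the mild end.

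Bias between arms is conditional. It needs Grade 1 shares that differ by arm, and the documents give no shares. Under the assumptions shown, the ratio of tested rates is between 1.00 and 0.62 when the truth is 1.00. That vaccination softens disease is a possibility and not a statement in the plan, so a reader should not conclude that the comparison will favour vaccine.

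The outcome is secondary and descriptive. Section 9.1.2 calls the study exploratory, and Section 9.5.1 confines formal comparisons to viral titers and antibody responses. No test, error rate or sample size changes. With single-digit expected cases per arm in the illustration at r = 0.30, however, one or two untested episodes would visibly change the summary, so the correction is worth making.

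**What to change.** Reconcile the surveillance row of Table 16 with Sections 3 and 6.6.2. One trigger for the nasal wash should cover every medically attended fever, URI, otitis media or LRI that the Section 9.2.2 outcome counts, at any grade, in both arms. It should apply in both seasons, since Section 6.7 carries the Section 6.6 procedures into the second.

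The cost is one table cell and, at most, a few visits that Sections 3 and 6.6.2 already require. The change concerns outcome ascertainment only.
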